Comparison of the ApneaLink Air Home Sleep Testing Device to Polysomnography

Investigational Plan

Protocol Number	SLP-17-10-01
Protocol Version and Date	Version 1.0 31 January 2018
Sponsor	ResMed Corp [name]
Sponsor Contact	[name] Medical Affairs [contact]

ClinicalTrials.gov ID: NCT03470493

This protocol has been written in accordance with current applicable guidelines (IDE for USA) as well as all other relevant additional references, medical and legal.

The information herein is confidential and the property of ResMed Corp. It is to be used in confidence for the conduct of the clinical trial according to written agreement.

PROTOCOL REVISION HISTORY

Version No. And Date	Section	Change	Rationale
Version 1.0 31Jan18	n/a	n/a	Original Release

Protocol Synopsis

Study Title	Comparison of the ApneaLink Air Home Sleep Testing Device to Polysomnography
PSG Central Scoring	University of Florida Health Sleep Disorders Center
Study Objectives	
Primary:
 
 Demonstrate the sensitivity in diagnosing Sleep Disordered Breathing (SDB) of the ResMed ApneaLink Air device (AL) compared to PSG is at least 0.825 when results are scored using the AASM 2012 Guidelines. 
Secondary:
 
 Compare AL and PSG numbers of predominant obstructive and predominant central events using the effort band and flow sensor per AASM 2012 and 2007 Guidelines Evaluate the AL capability to accurately calculate monitoring time per AASM 2012 and 2007 Guidelines Evaluate the AL capability to accurately score hypopneas using the AASM 2012 arousal criterion (using monitoring time) vs PSG scoring of hypopneas Estimate the positive likelihood ratio in diagnosing SDB of AL compared to PSG and evaluate it against a threshold of 5 per AASM 2012 and 2007 Guidelines
Study Design	This is a prospective, unblinded, open-label, single group study. All subjects will undergo concurrent ApneaLink Air testing and in-lab polysomnography.
Selection Criteria	
Inclusion Criteria
 
 Participant is 18 years of age or older Participant is willing to provide informed consent Participant is willing to participate in all study related procedures 
Exclusion Criteria
 
 Unable to cease PAP therapy during PSG (if currently using) Requires use of oxygen therapy during sleep Diagnosis of untreated clinically relevant sleep disorder (other than SDB) Pregnant Participant is unsuitable to participate in the study in the opinion of the investigator
Number of Participants	75 participants total at 2 US sites
Study Duration	Each participant's participation will be 1 night. The entire study is expected to take approximately 6 months, depending on recruitment rates.
Study Endpoints	
Primary endpoint:
 
 Sensitivity in diagnosing SDB of the AL device using AASM 2012 guidelines. 
Secondary endpoints:
 
 The number of predominant obstructive and predominant central events using the AL effort band and flow sensor vs. PSG per AASM 2012 and 2007 Guidelines Monitoring times from AL vs total sleep time from PSG per AASM 2012 and 2007 Guidelines Number of hypopneas using the AASM 2012 arousal criterion (using monitoring time) Positive likelihood ratio in diagnosing SDB using AASM 2012 and 2007 guidelines

Contents

1	DEFINITIONS	5
2	BACKGROUND AND RATIONALE	6
3	OBJECTIVES	7
3.1	PRIMARY OBJECTIVES	7
3.2	SECONDARY OBJECTIVES	7
4	METHODS AND MATERIALS	7
4.1	POPULATION/PARTICIPANT SELECTION	7
4.2	STUDY DESIGN	7
4.3	MEASURES TAKEN TO MINIMIZE BIAS	8
4.4	ENVIRONMENT OF CLINICAL STUDY	8
4.5	NUMBER OF STUDY SITES AND PARTICIPANTS	8
4.6	INCLUSION/EXCLUSION CRITERIA	8
4.7	CLINICAL DEFINITIONS	8
4.8	SAMPLE SIZE JUSTIFICATION	9
4.9	ENDPOINTS	10
4.10	INVESTIGATIONAL DEVICES	10
4.11	DATA COLLECTION METHOD AND STORAGE	11
4.11.1	Data Collection	11
4.11.2	Study Documentation	11
4.11.3	Query Generation	12
4.11.4	Data Storage	12
4.11.5	Inspection of Records	12
4.11.6	Study Files and Record Retention	12
4.11.7	Regulatory Documentation	12
4.11.8	Distribution of Results	13
4.12	CLINICAL STUDY PROCEDURES	13
4.13	INFORMED CONSENT	13
4.13.1	Participant Remuneration	14
5	STATISTICAL ANALYSIS METHODS	14
6	MONITORING	15
7	ADVERSE EVENT MANAGEMENT	15
8	NON-SIGNIFICANT RISK DETERMINATION	16

1 DEFINITIONS

ITEM	DEFINITION
ADE	Adverse Device Effect
AE	Adverse Event
AHI	Apnea Hypopnea Index - Number of apnea and hypopnea events per hour when total sleep time is used
AL	ApneaLink Air – ResMed’s FDA cleared HSAT type III device
BMI	Body Mass Index
CPAP	Continuous Positive Airway pressure
CSA	Central Sleep Apnea
eCRF	Electronic Case Report Form
EDC	Electronic Data Capture
HSAT	Home Sleep Apnea Testing
IRB	Institutional Review Board
Monitoring Time	Estimation of total sleep time by an HSAT device, e.g., ApneaLink Air
OSA	Obstructive Sleep Apnea
PSG	Polysomnography
REI	Respiratory Event Index – Number of apnea and hypopnea events per hour when calculated from an HSAT device
RERA	Respiratory Effort Related Arousal
SAE	Severe Adverse Event
SDB	Sleep Disordered Breathing
TST	Total Sleep Time - The amount of actual sleep time in a sleep episode; this time is equal to the total sleep episode less the awake time.

2 BACKGROUND AND RATIONALE

Sleep Disordered Breathing (SDB) is characterized by any abnormal breathing manifestation while asleep, including obstructive sleep apnea (OSA), central sleep apnea (CSA) and Cheyne-Stokes Respiration (CSR). Most recent data from the Wisconsin Sleep Cohort Study estimates sleep disordered breathing prevalence is 33.9% in males and 17.4% in females between the ages of 30 and 70¹. The prevalence of symptomatic OSA in the adult population has been estimated to be 4% in males and 2% in females². These patients demonstrate behavioral and neuropsychological consequences to varying degrees, including excessive daytime sleepiness, intellectual deterioration and depression³. More serious consequences include arterial systemic hypertension, arterial pulmonary hypertension and heart disease⁴.

The current gold standard for SDB diagnosis is in-laboratory polysomnography (PSG). The high demand for this labor intensive and time-consuming test results in patients waiting 2-10 months⁵ for an appointment. Over 80% of patients with OSA remain undiagnosed⁶ leaving the majority of the affected population with co-morbid consequences. The need for a diagnostic test that is more widely available and less expensive is necessary, not only to lessen the burden on sleep labs but also to provide patients with a diagnosis and treatment as soon as possible.

A barrier of acceptance of Home Sleep Apnea Testing (HSAT) devices as a diagnostic test is their inability to accurately measure total sleep time (TST)⁷. Currently most HSAT devices use monitoring time to calculate the respiratory event index (REI) as a surrogate for apnea hypopnea index (AHI). The need for TST determination from a HSAT device has been suggested to further validate and expand the use of HSAT devices. A novel algorithm developed by ResMed, Ltd. allows the AL device to accurately calculate TST, however, this algorithm has not yet been validated.

The ApneaLink Air (AL) device is a type III HSAT device. The device is capable of recording up to four channels of data including: flow and snore via a nasal cannula attached to a pressure transducer, a respiratory effort belt, a pulse oximeter to measure pulse and oxygen saturation, and an actigraphy monitor to measure TST along with flow. The AL device has been validated against PSG for AHI^{8,9} and Cheyne-Stoke respiration detection¹⁰. Further validation of the effort belt is necessary to determine the accuracy of the AL ability to differentiate between obstructive and central apneic events.

In 2012, the American Academy of Sleep Medicine (AASM) changed the criteria needed to score a hypopnea during a sleep study. Previous 2007 criteria had required a hypopnea to include a decrease in oronasal airflow by $\geq 30\%$ from baseline for at least 10 seconds and $\geq 4\%$ SpO₂ desaturation¹¹. These criteria have been widely accepted by healthcare providers to form the basis of reimbursement for patient equipment. In 2012, a change was made to these criteria which permitted hypopneas to be scored with an arousal only, or an oxygen desaturation of $\geq 3\%$. This change in rules significantly increases the percentage of patients who may now be diagnosed with OSA, potentially by up to 40%. The need for HSAT devices to detect sleep arousal is now evident with the 2012 AASM update. The AL contains software to detect respiratory effort related arousals (RERA) and score hypopneas using the new 2012 AASM arousal criterion, however, the algorithm has not been validated.

3 OBJECTIVES

The aim of this study is to evaluate the accuracy of the ResMed ApneaLink Air device (AL) as it compares to PSG. The AASM criteria for out-of-center testing devices are used to evaluate the accuracy of AL¹². Specifically, the sensitivity in diagnosing SDB of the ResMed ApneaLink Air device will be estimated per AASM 2012 guidelines and compared to the threshold of 0.825. Participants will use an AL device while undergoing concurrent PSG, which will be considered the gold standard for the estimate of sensitivity.

3.1 Primary Objectives

The primary objective is to show that the sensitivity in diagnosing SDB of the ResMed ApneaLink Air device is at least 0.825 when results are scored using the AASM 2012 Guidelines.

3.2 Secondary Objectives

The secondary objectives of the study are:

- Compare AL and PSG numbers of obstructive and central events using the effort band and flow sensor per AASM 2012 and 2007 Guidelines
- Evaluate the AL capability to accurately calculate monitoring time per AASM 2012 and 2007 Guidelines
- Evaluate the AL capability to accurately score hypopneas using the AASM 2012 arousal criterion (using monitoring time) vs PSG
- Estimate the positive likelihood ratio in diagnosing SDB of AL compared to PSG and evaluate it per AASM 2012 and 2007 Guidelines against the threshold of 5

4 METHODS AND MATERIALS

4.1 Population/Participant Selection

Eligible participants will be adults who are referred to a sleep lab for investigation of SDB. Only participants who meet the inclusion and exclusion criteria and sign the informed consent form (ICF) will be considered for enrollment.

4.2 Study Design

This is a prospective, non-blinded, open label, single arm study to evaluate the AL ability to correctly score SDB compared to the gold standard diagnostic tool, in-lab PSG. All participants will meet the inclusion and exclusion criteria and will sign the informed consent form before any study related procedures are performed. All participants will wear the AL device and undergo concurrent PSG testing. The AL and PSG tests will only be considered evaluable if the evaluation time is ≥ 4 hours. Participants with <4 hours evaluable time will be asked if they would like to repeat the test.

The AL device will be scored automatically using both AASM 2012 and 2007 guidelines. The AL automatic results will be compared with the PSG using all variables identified by the study objectives. These variables are defined in Section 4.7. Results collected in this study may be used for further algorithm and product development that are outside the scope of this protocol.

4.3 Measures Taken to Minimize Bias

A qualified sleep scientist who is approved to score sleep studies will score all PSGs. This individual will not have information about the participant's AL results.

4.4 Environment of Clinical Study

Recruitment, screening, and testing will occur in an accredited Sleep Lab.

4.5 Number of Study Sites and Participants

Up to 75 participants meeting the inclusion and exclusion criteria will take part in this study.

4.6 Inclusion/Exclusion Criteria

Inclusion Criteria

- Participant is 18 years of age or older
- Participant is willing to provide informed consent
- Participant is willing to participate in all study related procedures

Exclusion Criteria

- Unable to cease PAP therapy during PSG (if currently using)
- Requires use of oxygen therapy during sleep
- Diagnosis of uncontrolled clinically relevant sleep disorder (e.g., untreated insomnia or restless leg syndrome)
- Pregnant
- Participant is unsuitable to participate in the study in the opinion of the investigator

4.7 Clinical Definitions

AHI/REI

Following AASM guidelines, an apnea will be scored when there is a drop in the peak signal excursion by $\geq 90\%$ of pre-event baseline and the duration of the $\geq 90\%$ drop in sensor signal is ≥ 10 seconds.

Both 2007 and 2012 AASM definitions for hypopnea will be used:

AASM 2007 - A hypopnea will be scored when the peak signal excursions drop by $\geq 30\%$ of pre-event baseline, the duration of the $\geq 30\%$ drop in signal excursion is ≥ 10 seconds and there is a $\geq 4\%$ oxygen desaturation from pre-event baseline.

AASM 2012 - A hypopnea will be scored when the peak signal excursions drop by $\geq 30\%$ of pre-event baseline, the duration of the $\geq 30\%$ drop in signal excursion is ≥ 10 seconds and there is a $\geq 3\%$ oxygen desaturation from pre-event baseline or the event is associated with an arousal.

AHI

Apnea-hypopnea Index is derived from apneas plus hypopneas per hour of total sleep time from a PSG.

REI

Respiratory Event Index is derived from apneas plus hypopneas per hour of monitoring time from an HSAT.

OAI

Following AASM guidelines, an apnea will be scored as obstructive if it meets apnea criteria and is associated with continued or increased inspiratory effort throughout the entire period of absent airflow. The use of both the monitoring time and total sleep time will be used for OAI calculation and comparison.

CAI

Following AASM guidelines, an apnea will be scored as central if it meets apnea criteria and is associated with absent inspiratory effort throughout the entire period of absent airflow. The use of both the monitoring time and total sleep time will be used for CAI calculation and comparison.

Mixed apneas

Following AASM guidelines, an apnea will be scored as mixed if it meets apnea criteria and is associated with absent inspiratory effort in the initial portion of the event, followed by resumption of inspiratory effort in the second portion of the event.

TST

Total Sleep Time as defined as sum of all sleep epochs from PSG between lights off and lights on.

Monitoring Time

Estimation of total sleep time by an HSAT device.

RERA

Following AASM guidelines, an event will be scored as a respiratory event related arousal (RERA) if during the diagnostic study there is a sequence of breaths lasting at least 10 seconds characterized by increasing respiratory effort or by flattening of the inspiratory portion of the nasal pressure leading to an arousal from sleep when the event does not qualify as an apnea or hypopnea.

4.8 Sample Size Justification

The sample size for this clinical study will be up to 75 eligible participants undergoing PSG.

Recruitment goals are as follows:

- At least 30 men and at least 30 women
- At least 5 participants in each of the following SDB categories (per PSG):
 - No SDB (AHI <5)
 - Mild SDB (AHI 5-14)
 - Moderate SDB (AHI 15-29)
 - Severe SDB (AHI ≥ 30)
- At least 5 participants with CSA
- At least 5 participants in each of the following BMI categories (applies to both men and women):
 - Normal BMI: < 25.0
 - Overweight BMI: 25.0 – 29.9
 - Obese: ≥ 30
- At least 5 participants in each of the following race categories:
 - White
 - Black
 - Asian

The primary objective of this study is to demonstrate the sensitivity in diagnosing SDB per the AASM 2012 guidelines. Sensitivity will be assessed according to the AASM criteria for out-of-center testing devices. The hypotheses tested are:

$$H_0: \pi \leq 0.825 \text{ versus } H_A: \pi > 0.825$$

where π is the sensitivity of AL in diagnosing SDB (using a cut-off of 5 events per hour as the threshold for SDB and AHI from PSG and REI from HSAT). The hypothesis will be tested with an exact binomial test using a one-sided significance level of 0.025.

The required sample size to achieve 80% power was estimated using PASS 14, Tests for One Proportion Procedure, assuming a true sensitivity of 0.95 (13 out of 13 true positives were correctly classified in a previous study). To achieve an 80% probability of rejecting the null hypothesis, a minimum of 56 SDB participants are required. Seventy-five participants will be enrolled in order to meet recruitment goals.

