5 STATISTICAL ANALYSIS METHODS

Analysis Populations:

All subjects who meet the inclusion and exclusion criteria and who complete at least 4 evaluable hours will be included in the Intention-to-Treat population (ITT). All primary and secondary analyses will be generated for the ITT population.

Primary Analysis:

The diagnostic sensitivity of AL will be estimated as the number of participants with REI \geq 5 events per hour according to AL per AASM 2012 Guidelines divided by the number of participants with AHI \geq 5 events per hour according to PSG. The diagnostic sensitivity of AL will be compared to the threshold of 0.825 (AASM criteria for out-of-center testing devices) with an exact binomial test, using a significance level of 0.025. Further a one-sided 97.5% confidence interval for the diagnostic sensitivity will be calculated using the Wilson score method.

Secondary Analyses:

To compare the numbers of predominant obstructive and predominant central events measured by AL and PSG, each patient will be classified as having (1) fewer than 5 events per hour, (2) 5 to 10 events per hour, (3) 10 to 30 events per hour or (4) more than 30 events per hour. The categories obtained by AL and PSG will be compared with the weighted kappa statistic. Events will be assessed per both the AASM 2012 and 2007 guidelines.

To compare the AL monitoring times to the PSG total sleep times, Bland-Altman plots will be constructed and the 95% limits of agreement will be calculated. Times will be assessed per both the AASM 2012 and 2007 guidelines.

To compare the number of hypopneas measured by AL and PSG, the number of hypopneas per hour will be categorized as follows: (1) fewer than 5 events per hour, (2) 5 to 10 events per hour, (3) 10 to 30 events per hour or (4) more than 30 events per hour. The categories obtained by AL and PSG will be compared with the weighted kappa statistic. Events will be assessed per both the AASM 2012 and 2007 guidelines.

The positive likelihood ratio (the estimated sensitivity divided by 1 minus the estimated specificity) will also be calculated along with the associated one-sided 97.5% confidence interval. The positive likelihood ratio will be compared with the threshold of 5 (AASM criteria for out-of-center testing devices¹²) using a Wald test. The positive likelihood ratio will be calculated per the AASM 2012 and 2007 guidelines.

AEs

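### The banded kappa planned for central and obstructive events does not test whether AL labels apneas correctly, and the guaranteed CSA group of 5 may leave little information on central events

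*Combined protocol and SAP*

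**What the plan says.** Section 2 states the need: "Further validation of the effort belt is necessary to determine the accuracy of the AL ability to differentiate between obstructive and central apneic events". The matching secondary objective in section 3.2 is worded in terms of counts: "Compare AL and PSG numbers of obstructive and central events using the effort band and flow sensor per AASM 2012 and 2007 Guidelines".

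Section 5 sets the analysis: "To compare the numbers of predominant obstructive and predominant central events measured by AL and PSG, each patient will be classified" into one of four bands (below 5, 5 to 10, 10 to 30, above 30 events per hour). Then: "The categories obtained by AL and PSG will be compared with the weighted kappa statistic". No weights, confidence interval or success criterion are given for this kappa. The analysis set is everyone with at least 4 evaluable hours, because "All primary and secondary analyses will be generated for the ITT population".

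Section 4.8 caps enrolment: "The sample size for this clinical study will be up to 75 eligible participants undergoing PSG". Among the recruitment goals it lists "At least 5 participants with CSA". The documents do not say who counts as a CSA participant, how many are expected, or why 5 was chosen. Section 4.7 defines obstructive, central and mixed apneas separately, and the OAI and CAI.

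**The concern.** Differentiation is a question about labels: when PSG calls an apnea central, does AL do so too? Section 5 compares two participant-level rates, each cut into four bands. Two devices can agree on the bands while disagreeing on many of the underlying labels.

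The central-event kappa may also rest on few people. If most participants have fewer than 5 central events per hour on both devices, they all fall in the same cell of the table, and the kappa depends mainly on the few above that cut and on any false central readings. A high value could then be reported as validation of the effort belt when labels had not been compared, although AL and PSG are recorded at the same time.

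**Working it through.** **The plan's own figure.** Section 4.8 requires 56 SDB participants for the primary test (exact binomial, null 0.825, true sensitivity 0.95, one-sided 0.025, power 80%). With n = 56 and success at 52 or more correct, the type I error is 0.0229 and the power 0.853. No smaller n reaches 80% (the nearest, n = 48, gives 0.782), so 56 reproduces. It says nothing about the central and obstructive comparison, for which no size or precision is stated.

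**What the bands miss.** Two constructed participants, using the section 5 bands:

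| Case | PSG obstructive / central per hour | AL obstructive / central per hour | Bands (obstructive, central) | Labels |
|---|---|---|---|---|
| Within-band error | 35 / 4 | 39 / 0 | 4 and 1 on both devices | 0 of 4 central correct |
| Balanced swap | 12 / 8 | 12 / 8 | 3 and 2 on both devices | 4 of 20 correct, 0 of 8 central |

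In the first, AL calls all 4 central events obstructive (35 + 4 = 39). In the second, AL calls all 8 central events obstructive and 8 of the 12 obstructive events central, so AL's obstructive rate is 12 − 8 + 8 = 12, its central rate is 8 − 8 + 8 = 8, and 12 − 8 = 4 labels are right. Kappa records perfect agreement in both.

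**What the bands detect.** Assumption A: 75 evaluable participants, 70 in central band 1 on PSG and 5 in bands 2, 2, 3, 3 and 4. Linear weights are also assumed, since the plan names none. Then

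kappa = 1 − Σ|i − j|·O_ij / Σ|i − j|·E_ij, with E_ij = (PSG total in band i) × (AL total in band j) / 75.

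If AL is right on the 5 but puts some of the other 70 into a higher central band:
- 5 moved to band 2: 1 − 5/21.40 = 0.77
- 10 moved to band 2: 1 − 10/25.73 = 0.61
- 10 moved to band 3: 1 − 20/34.93 = 0.43

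False central labels that cross the cut therefore do lower kappa, including in participants without CSA.

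**How thin the upper bands could be.** Keep assumption A, with the other 70 in band 1 on both devices, and let AL put some of the 5 into band 1. The result depends on which ones. For two missed:
- both band 2 participants: AL totals are 72, 0, 2, 1; observed 1 + 1 = 2, expected 1150/75 = 15.33; kappa = 1 − 2/15.33 = 0.87
- one band 3 and the band 4 participant: AL totals are 72, 2, 1, 0; observed 2 + 3 = 5, expected 939/75 = 12.52; kappa = 1 − 5/12.52 = 0.60

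| Missed of 5 | Lowest kappa | Highest kappa |
|---|---|---|
| 0 | 1.00 | 1.00 |
| 1 | 0.79 | 0.94 |
| 2 | 0.60 | 0.87 |
| 3 | 0.35 | 0.71 |
| 4 | 0.19 | 0.49 |
| 5 | 0.00 | 0.00 |

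Raw agreement is still 70/75 = 93.3% when all 5 are missed.

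**Precision with 5.** Exact (Clopper-Pearson) 95% intervals: 3 of 5 detected, 15% to 95%; 5 of 5, 48% to 100%.

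**The case against.** The strongest reply is that the objective and endpoint concern numbers of events, and section 5 analyses numbers. Label accuracy appears only in the background, the objective is descriptive, and no hypothesis is attached to it. That is right as far as it goes, and it limits how serious the point is. But section 2 gives differentiation as the reason for the work, and the planned analysis does not answer that directly.

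Three stronger readings are tempting, and the documents do not support them.

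- That central-event agreement will rest on about 5 people. Five is a floor. The expected number is not given, CSA is not defined by a rate, and participants outside that group may have 5 or more central events per hour.
- That mislabelling in participants without CSA is never seen. All evaluable participants enter the kappa, and false central labels that cross a boundary lower it, as shown above.
- That the trial cannot address the question at all. The kappa gives indirect evidence: under assumption A it falls to 0 if AL misses all 5. Raw AL files and PSG EDF files are also collected. The limit lies in the planned analysis.

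Nor should 0.87 be quoted alone for two missed. It is the best case, in which AL misses the two mildest participants.

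An objection to the remedy also stands in part. The central share, CAI/(CAI + OAI), is itself a participant-level summary: in the balanced-swap case it is 8/20 = 0.40 on both devices. It is unstable with few apneas, since one central of two already gives 50%. Only matching events detects balanced swaps, and that needs aligned clocks and timed AL event labels, which sections 4.11.1 and 4.12 do not mention.

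**Conclusion.** The concern holds in limited form. A high weighted kappa on the section 5 bands would not by itself show that AL labels apneas correctly, because errors within a band and errors that cancel go undetected. This follows from the banding and needs no assumption about CSA numbers. Errors that cross a band boundary are detected.

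The thinness of the central data is a possibility, conditional on the number staying near the floor of 5. The kappa range of 0.60 to 0.87 for two missed rests on the assumed 70/5 split, the assumed spread over bands and linear weights. The 15% to 95% interval depends only on the counts of 3 and 5. The point merits a change to the plan, but it affects one secondary objective only; the primary sensitivity analysis is untouched.

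**What to change.** In section 5, keep the banded kappa, state its weights and interval, and add:

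- **(a) In all evaluable participants:** AL minus PSG differences in unbanded CAI and OAI, with mean difference and 95% limits of agreement. In the within-band case above these would show −4 and +4 per hour. Add the central share of classified apneas by each device, either pooled or limited to participants with a pre-stated minimum number of apneas.
- **(b) Where AL and PSG recordings can be time-aligned:** a descriptive cross-table of central, obstructive and mixed labels for matched apneas, with participant-level bootstrap intervals. Pre-state the matching rule and report how many participants and apneas could not be matched.

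In section 4.8, say who counts as a CSA participant, and state that agreement within this group is descriptive if the number stays near 5.

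The cost is wording and some programming, with no extra participants. Part (a) uses indices already defined in section 4.7. Part (b) depends on clock alignment and on obtaining timed AL event labels, so its feasibility should be confirmed before it is promised. Intervals may be wide if central apneas are few, and the report should show that.
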